6.6 Delay in performing non cardiac surgical procedure

The delay in performing cardiac and non cardiac surgical procedures will be defined as the time from the time of surgical indication to the time of surgical procedure.

7. STATISTICS

7.1 The Number of Participants

Consecutive patients will be enrolled over one year of time at the participating Centers.

Cases and controls patients will be divided into those who will use Consensus Document “Stent and Surgery-2” (group 1) vs those who traditionally will be managed by local practice (group 2). On the basis of previous data reported SAS, a sample size of 1623 patients would be required to have a case-control matching 1:2, assuming a study power of 80% and 5% significance. Of those, 324 case-patients (20% of group 1) vs 162 control-patients (ratio 1:2) would be required for enrollment within one-year after implanted stents. Two preplanned interim analyses will be performed by an independent statistician when 800 and 1500 of patients will be enrolled.

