3. OBJECTIVES

3.1 Primary Objective

- To assess outcomes associated with the application of the Consensus Document “Stent and Surgery-2” on perioperative antiplatelet therapy in patients with coronary stenting undergoing surgery.

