4. STUDY DESIGN

4.1 Summary of Study Design

The SAS registry will include any patient with previous coronary stenting undergoing any type of surgery or operative endoscopic/endovascular procedure at the participating Centers. Centers will be divided into two groups: Centers that routinely follow the recommendations of the SAS 2 Document and Centers that do not. The relevant clinical, procedural and outcome data (within index admission and at 30 days) will be entered in a specifically designed electronic case record form (eCRF).

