4.2 Primary endpoint

- Rate of discontinuation of P2Y12 inhibitors and/or aspirin (without bridging) in the first 3 months after PCI with low risk characteristics and 6 months after PCI with high risk characteristics or any antiplatelet therapy discontinuation without bridging therapy

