7.2 Description of Statistical Methods

Continuous numeric variables will report as means with SD and compared using the Student’s t- or Wilcoxon rank-sum test. Categorical variables will be presented as counts and percentages and will be compared using the chi-square or Fisher’s exact test. To examine the effect of significant factors on two different groups (Group 1 vs Group 2) the hazard ratio of the interaction term will be calculated. To identify the independent predictors for in hospital NACE, 30day MACE and 30-day BARC bleedings, first univariate and then multivariate logistic regression models will apply. The BARC bleedings will be considered according to type of surgery. Specifically, BARC bleedings grade ≥ 3 will be considered in patients undergoing cardiac surgery, and BARC bleedings grade ≥ 4 will be taken into account for non-cardiac surgery. Covariates for multivariable models will be selected on the basis of a backward stepwise algorithm in a Cox proportional hazards model. Additionally, to minimise group differences on confounding covariates between patients who will be managed with consensus document (group 1) and those who will be received local practice (group 2), a 1:2 propensity score matching would be used. Propensity scores will be calculated with logistic regression, with multiple imputation and backwards elimination with a significance level to stay of 0.05. To ensure that the comparison between two groups (group 1 vs group 2) would not be bias, the proportion of patients who will not received consensus document within center that traditionally used it, will be excluded. The results will be presented as ORs with 95% confidence intervals (CI) and p values. For all

analyses, a two-sided $P <0.05$ will be required for statistical significance. All data will be analyzed using the Statistical Package of Social Sciences version 20 (IBM SPSS, Chicago, IL).

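### Section 4.1 forms the comparison groups by centre, 7.1 and 7.2 by how each patient was managed, and 7.2 excludes on one side only, so the control group is not uniquely defined.

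*Combined protocol and SAP*

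**What the plan says.** - **Section 4.1 (unit: the centre).** "Centers will be divided into two groups: Centers that routinely follow the recommendations of the SAS 2 Document and Centers that do not".
- **Section 7.1 (unit: the patient).** Patients for whom the Document is used form group 1, "vs those who traditionally will be managed by local practice (group 2". The total of 1623, the 1:2 matching and the 80% power at 5% significance are stated for this comparison.
- **Section 7.2, matching sentence (unit: the patient's management).** Propensity matching is to reduce confounding "between patients who will be managed with consensus document (group 1) and those who will be received local practice (group 2".
- **Section 7.2, exclusion sentence (centre and patient combined).** To avoid bias, "the proportion of patients who will not received consensus document within center that traditionally used it, will be excluded". There is no mirror rule for patients managed with the Document at other centres.
- **Section 3.1.** The aim is "To assess outcomes associated with the application of the Consensus Document", with no statement of whether a centre or a patient applies it.
- **Section 4.2.** The primary endpoint begins "Rate of discontinuation of P2Y12 inhibitors and/or aspirin (without bridging) in the first 3 months after PCI with low risk characteristics" and goes on to cover any antiplatelet discontinuation without bridging.

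**The concern.** The comparison is not randomised, so the rule that forms the groups largely determines what is estimated. A centre rule asks what follows from a centre's routine policy. It keeps the team's choice for the individual patient out of the exposure, at the price of dilution by crossovers. A patient rule asks what follows from being managed with the Document, and lets that individual choice set the group. These are different questions with different control groups, and the plan does not say which is primary.

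The choice matters more here because the primary endpoint is a perioperative management decision. A patient judged not managed with the Document may be so judged because of the therapy given. The variables listed in section 4.5.3 include no item recording whether the Document was used for a patient. If use is inferred from observed therapy, exposure and outcome overlap. Excluding such patients at SAS 2 centres alone can then remove endpoint events from group 1 and leave group 2 untouched.

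**Working it through.** **1. Classification under each section**

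| Centre | Patient managed with the Document? | 4.1 | 7.1 and 7.2 matching sentence | 7.2 exclusion sentence |
|---|---|---|---|---|
| SAS 2 | yes | group 1 | group 1 | kept |
| SAS 2 | no | group 1 | group 2 | excluded |
| Other | yes | group 2 | group 1 | not addressed |
| Other | no | group 2 | group 2 | kept |

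The first and last rows agree throughout. The second row carries three labels and the third carries two.

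**2. The plan's own figures.** The total of 1623 can be neither reproduced nor refuted, because section 7.1 gives no event rates or effect size. A 1:2 split is 1623/3 = 541 against 1082. The 80% power at two-sided 5% implies a standardised effect of 1.960 + 0.842 = 2.80.

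**3. Power, if the 80% was set for the patient contrast and the groups are formed by centre.** With total crossover x, the effect shrinks to 2.80(1 − x), and power = P(|Z + 2.80(1 − x)| > 1.96). Crossover is an assumption, and patients are treated as independent.

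| x | Effect | Power |
|---|---|---|
| 0 | 2.80 | 80% |
| 6% | 2.63 | 75% |
| 10% | 2.52 | 71% |
| 20% | 2.24 | 61% |

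**4. How the choice of rule can move the result (assumed rates, crude comparison).** Take 541 patients at SAS 2 centres and 1082 at other centres. Assume the same overall endpoint rate in both, so the centre-level odds ratio (OR) is 1.00, and no use of the Document at other centres. Let a share u of SAS 2-centre patients not be managed with the Document, with an endpoint rate of 10% if managed and 40% if not.

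For u = 10%:
- Overall rate: 0.9 × 0.10 + 0.1 × 0.40 = 13%, in both centre types.
- By patient management: group 1 has 10%. Group 2 has (1082 × 0.13 + 54.1 × 0.40)/1136.1 = 14.3%. OR = 0.67.
- With the 7.2 exclusion: 10% against 13%. OR = 0.74. The exclusion removes 54.1 × 0.40 = 21.6 of 541 × 0.13 = 70.3 expected events from group 1, and none from group 2.

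| u | Centre rule | Patient rule | 7.2 exclusion |
|---|---|---|---|
| 10% | 1.00 | 0.67 | 0.74 |
| 20% | 1.00 | 0.50 | 0.58 |
| 30% | 1.00 | 0.40 | 0.47 |

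If the endpoint rate does not depend on management, all three rules give 1.00. If the two rates are swapped (40% managed, 10% not) at u = 10%, the overall rate is 0.9 × 0.40 + 0.1 × 0.10 = 37%, and the exclusion gives (0.40/0.60)/(0.37/0.63) = 1.14. The direction therefore depends on rates that the documents do not give.

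**The case against.** The strongest reply is that the sections can be read together. Under a purely patient-level rule, a patient not managed with the Document would simply be group 2 and would need no exclusion. The exclusion sentence therefore presupposes the centre groups of 4.1, and the word traditionally in 7.1 points the same way. On that reading, group 1 is patients at SAS 2 centres who were managed with the Document, and group 2 is patients at the other centres. This is coherent, but the plan never states it, and it leaves unassigned the patient managed with the Document at another centre. That patient is plausible: section 5 offers the app to the investigators without limiting it to one centre group. The reading also keeps the one-sided exclusion.

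A second reply is that propensity matching handles confounding. Matching works on groups already formed, so it cannot decide who belongs in which. It may reduce confounding through measured covariates, but it does not return excluded patients to group 1.

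A third reply is that a centre-level primary comparison is a preference, since section 3.1 names no unit. That is fair. Reconciling the text does not by itself require the centre rule, and that rule brings clustering and centre-level confounding to the fore. It is still the rule already in the design section and the one that keeps the outcome-related choice out of the exposure.

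Three stronger inferences are not supported:
- **That any crossover patient can be group 1, group 2 or excluded.** This holds only for the patient not managed with the Document at a SAS 2 centre.
- **That the patient rule biases 30-day events by a known amount.** One can construct crude ORs of 1.14 to 1.64 by moving 5% to 20% of local-practice patients into group 1. That requires every mover to be high-risk, uses assumed rates for a non-primary endpoint, and ignores the planned matching.
- **That the study is underpowered.** The power loss arises only if the 80% was set for the patient contrast, which section 7.1 does not say.

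**Conclusion.** The concern holds as an unresolved contradiction about who is compared with whom. It should be settled before any comparative analysis, including the interim analyses. The classification conflict follows from the text and needs no assumption. That management-based grouping or the one-sided exclusion can move or remove primary endpoint events follows from the nature of the endpoint. How far, and in which direction, cannot be computed from the documents; the ORs in the working show the mechanism on assumed rates and are not estimates. The power figures of about 71% and 61% are conditional on the 80% having been set for the patient contrast, on assumed crossover of 10% and 20%, and on no clustering.

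**What to change.** 1. Use one rule in 4.1, 7.1 and 7.2. For the primary comparison, apply the centre rule already in 4.1: record each centre's status before its first patient, keep every patient in the centre's group, and do not revise status on observed management.
2. Use standard errors that allow for clustering by centre, since exposure is then constant within a centre.
3. Report the managed-with-the-Document contrast, including the 7.2 exclusion, as a labelled secondary analysis. Define management with the Document in the same way in both centre groups, and state how it is ascertained.
4. State in 7.1 which contrast the 80% refers to. If it was the patient contrast, restate it for the centre contrast, for expected crossover and for clustering.
5. Acknowledge that confounding by centre remains: centres that adopt the Document may differ in case mix and practice.

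**Cost.** Wording in three sections, a record of each centre's status at initiation, and a per-patient item on use of the Document. The price is a diluted contrast, wider intervals from clustering and a less favourable stated power. The change does not itself require more patients. If the sponsor wished to restore 80% after dilution, ignoring clustering, the total would be 1623/0.9² ≈ 2,004 at 10% crossover and 1623/0.8² ≈ 2,536 at 20%.

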4.4 Participants

4.4.1 Inclusion Criteria

Eligible will be male and female patients > 18 years of age.

Eligible will be patients with previous coronary stenting undergoing any kind of surgical or operative endoscopic procedure at the participating Centers, irrespective of the distance in time between stenting and surgery.

Both candidates to elective and urgent/emergent surgical procedures will be included in the MONET registry.

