6. DEFINITIONS OF THE ENDPOINT COMPONENTS

6.1 Antiplatelet therapy discontinuation

Antiplatelet discontinuation is defined as P2Y₁₂ inhibitors and/or aspirin withdrawal for >5 days at the time of surgical procedure without bridging therapy with antiplatelet agents in the first 3 months after PCI with low risk characteristics and 6 months after PCI with high risk characteristics or any any antiplatelet therapy discontinuation without bridging therapy at any time after PCI. A detailed description on the perioperative management of oral antiplatelet therapy will be obtained for both aspirin and P2Y₁₂ inhibitors (ticlopidine, clopidogrel, prasugrel, and ticagrelor). This includes the time delay from drug interruption to surgery as well as the time from surgery to reintroduction of therapy. The use of any bridging strategy will also be recorded. According to the SAS 2 Consensus Document, in selected patients at high risk for both bleeding and ischemic events, when withdrawal of oral antiplatelet therapy is required, bridging with cangrelor or with a short-acting intravenous glycoprotein IIb/IIIa inhibitor (GPI) (tirofiban or eptifibatide) can be considered.

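### The sample-size counts in section 7.1 contradict each other, and the inputs behind the 80% power are not given

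*Combined protocol and SAP*

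**What the plan says.** Section 7.1 (The Number of Participants) defines group 1 as patients managed with the consensus document and group 2 as patients managed by local practice: "Cases and controls patients will be divided into those who will use Consensus Document" and those who will not. Citing earlier SAS data in general terms, it says that "a sample size of 1623 patients would be required to have a case-control matching 1:2, assuming a study power of 80" percent and 5% significance. It then draws a subset from that total: "Of those, 324 case-patients (20% of group 1) vs 162 control-patients (ratio 1:2) would be required for enrollment within one-year" of stent implantation. It also says that "Two preplanned interim analyses will be performed by an independent statistician when 800 and 1500 of patients will be enrolled".

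Section 7.2 repeats the ratio for the analysis, where "a 1:2 propensity score matching would be used", and sets two-sided P<0.05 for all analyses.

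Section 4.2 names a primary endpoint, which begins "Rate of discontinuation of P2Y12 inhibitors and/or aspirin (without bridging) in the first 3 months after PCI with low risk characteristics". Neither the population nor the endpoint is limited to one year after stenting. Section 4.4.1 takes patients "irrespective of the distance in time between stenting and surgery", and the definition in section 6.1 extends to "antiplatelet therapy discontinuation without bridging therapy at any time after PCI".

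**The concern.** Section 7.1 is the plan's only sample-size statement. It gives a total, a subset count for each group, a percentage with a named base, and a ratio. A reader should be able to get from any of these to the others, and cannot. The number needed in each group, overall and within one year of stenting, is therefore unknown.

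The 80% power has a separate problem. Power, significance level and sidedness are given, but the endpoint it refers to, the expected control rate and the difference to be detected are not. It is also unclear whether the power belongs to all patients or to the one-year subset. The 80% is attached to 1,623, yet required counts are then set for the subset. A null result could not be read against any stated detectable difference.

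The ratio direction also matters beyond section 7.1, because section 7.2 makes 1:2 matching part of the group comparison.

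**Working it through.** **Inputs.** From 7.1: total 1,623; 324 cases, stated to be 20% of group 1; 162 controls; ratio 1:2; 80% power; 5% significance; interim looks at 800 and 1,500. From 7.2: two-sided testing. The plan gives no event rates, so its 1,623 cannot be reproduced.

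**1. The printed figures taken together.**
- Group 1 = 324/0.20 = 1,620. Left for group 2: 1,623 − 1,620 = 3, against 162 required.
- Allowing for rounding of the 20%: at 20.5%, group 1 = 324/0.205 ≈ 1,580, leaving about 43. At 19.5%, group 1 ≈ 1,662, more than the total.

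**2. Any split of 1,623.** Group 2 ≥ 162 gives group 1 ≤ 1,623 − 162 = 1,461, and 0.20 × 1,461 = 292.2 < 324.

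**3. The obvious splits.**

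| Group 1 | 20% of group 1 |
|---|---|
| 541 (one third) | 108.2 |
| 811.5 (half) | 162.3 |
| 1,082 (two thirds) | 216.4 |
| 1,623 (the whole total) | 324.6 |

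Only the last line gives 324, so either the base of the 20% is wrong or 1,623 is not the total.

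**4. Ratio.** 324/162 = 2.0, which is 2:1 in the order written. It is 1:2 only if read as control:case, and the 20% still fails in step 1.

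**5. Candidate repairs.** The text does not choose between them.
- One-year subset: 108 + 216 = 324; 162 + 324 = 486 (either direction); or 324 + 648 = 972.
- Total: 1,623; or, if 1,623 is group 1 alone, 1,623 × 1.5 ≈ 2,434 (half as many controls) or 1,623 × 3 = 4,869 (twice as many).

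**6. Can the missing inputs be inferred from N?** No. A search over whole-percent rates, both ratio directions, two-sided 5%, 80% power and no continuity correction found 34 combinations with a total within 3% of 1,623 (for example 3% vs 6%, 11% vs 16%, 30% vs 37%). It found 45 within 3% of 486 (for example 9% vs 18%, 15% vs 26%).

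**7. What the ambiguity is worth (illustration; control rates assumed).** With d = |p1 − p2| and p̄ the pooled rate:

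power = Φ{[d − 1.96·√(p̄(1−p̄)(1/n1+1/n2))] / √(p1(1−p1)/n1 + p2(1−p2)/n2)}

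| Group 1 vs group 2 | Detectable reduction from 20%, points | Detectable reduction from 30%, points | Power for 20.0% vs 14.4% (d = 5.61 points) |
|---|---|---|---|
| 541 vs 1,082 | 5.61 | 6.55 | 0.800 |
| 1,082 vs 541 | 5.52 | 6.49 | 0.813 |
| 324 vs 648 | 7.13 | 8.38 | 0.575 |
| 324 vs 162 | 9.49 | 11.40 | 0.358 |
| 162 vs 324 | 9.78 | 11.62 | 0.320 |
| 108 vs 216 | 11.69 | 14.01 | 0.224 |

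Example, 324 vs 162: p̄ = (324 × 0.1439 + 162 × 0.20)/486 = 0.1626. The two standard errors are 0.0355 and 0.0370. (0.0561 − 1.96 × 0.0355)/0.0370 ≈ −0.36, so power ≈ 0.36.

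**8. Interim looks (secondary).** Suppose the looks at 800 and 1,500 and a final look at 1,623 each tested the groups at unadjusted two-sided 5%, with information proportional to enrolment (0.493, 0.924, 1). The overall type I error would be about 9.3%.

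**The case against.** **One reading rescues the counts.** If 1,623 is group 1 alone and controls are half as many (about 812), then 20% of group 1 is 324.6 and 20% of group 2 is 162.3. Both counts, the stated base of the 20% and a control:case ratio of 1:2 then agree. The error would lie in the total, not in the 20%, and the same 5.6-point reduction would have about 93% power in the full sample. This is the best alternative, and it shows that the proof in steps 1 and 2 depends on 1,623 being the total. But the text calls 1,623 the sample size and draws both cases and controls from it. The last interim at 1,500 also fits a total of 1,623 far better than one of about 2,434. Even under this reading the plan misstates its total.

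**The range of 22% to 58% uses counts the plan does not print.** That is correct. Its ends come from 108 vs 216 and 324 vs 648. The printed pair gives 32% to 36%. The plan also never says that a hypothesis is tested in the one-year subset, so the subset figures show what could follow, not a demonstrated loss.

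**Nothing operational depends on these numbers.** Accrual is consecutive over 12 months, and no test in section 7.2 uses 324, 162 or the 20%. This limits the harm, but it does not make a contradictory sample-size statement acceptable.

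**The interim looks are a separate matter.** The plan does not say that they compare the groups. The point is kept only as a clarification, and the conclusion does not rest on it.

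**Conclusion.** The concern holds. With 1,623 as the total, which is what the text says, 324 cases as 20% of group 1 leave 3 patients for group 2 against 162 required, and no split of 1,623 removes the conflict. The ratio is reversed in the order written. The 80% power cannot be checked, because no endpoint, control rate or difference is linked to it.

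The contradiction rests on the plan's own figures and needs no outside assumption. The size of the consequence does rest on assumptions. With control rates of 20% or 30%, the smallest detectable reduction is about 5.5 to 6.6 points for a 1:2 or 2:1 split of 1,623, and about 7.1 to 14.0 points in the one-year subset, depending on the reading. These figures are optimistic. They treat patients as independent although section 4.1 sets the group by centre, and they assume that everyone is analysed although section 7.2 excludes some patients and matches the rest.

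This must be corrected because the stated sample size is impossible as printed. It affects the justification and the reading of precision, not who is enrolled or how patients are treated.

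**What to change.** Rerun the calculation from the earlier registry data that section 7.1 relies on. If those data do not supply usable inputs, say so and state the assumptions used. Then restate in section 7.1:

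- the total, and the numbers in group 1 and group 2;
- the one-year subset count in each group, and the base of the 20%;
- one ratio direction, written as group 1:group 2 and used identically in section 7.2;
- the endpoint, control rate and difference behind the 80%;
- whether the power applies to all patients or to the one-year subset;
- the power or detectable difference that the corrected full sample and subset deliver.

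Enrolment stays at 12 months and need not be enlarged.

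As a secondary clarification, state that the looks at 800 and 1,500 are descriptive with no between-group claim. If they do test the groups, adopt an alpha-spending rule.

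The cost is protocol and SAP wording plus one rerun calculation. The downside is that the restated numbers and the subset precision may look less favourable than the present text suggests.

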4.4.3 Enrolment time

The enrolment period is 12 months after authorization of respective Ethics Committee.

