4.5.4 Follow-up

A follow-up contact visit is planned at 30 days (\pm 7 days) after the surgical procedure using hospital records, outpatient visits, or telephone contact. A standard questionnaire will be used to collect information on the medications the patients were taking and the occurrence of any adverse events. Each site will have a designated individual who entered raw data into an electronic case report form, allowing immediate and continuous monitoring of its completeness and accuracy. Unscheduled visits can also take place whenever necessary.

Relevant information to be inquired and collected in the e-CRF will include:

- check of items describing the primary and secondary study endpoints, with special reference to new hospitalizations;
- ongoing medications
- compliance with medication prescribed at discharge
- adverse events

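### Two interim looks, the second at 92% of the target, have no adjustment for repeated testing; if each is tested at 0.05, overall type I error is about 9.3%, not 5%

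*Combined protocol and SAP*

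**What the plan says.** Section 7.1 (The Number of Participants) states that "a sample size of 1623 patients would be required to have a case-control matching 1:2", "assuming a study power of 80% and 5% significance". It then adds: "Two preplanned interim analyses will be performed by an independent statistician", and fixes the timing as "when 800 and 1500 of patients will be enrolled".

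Section 7.2 (Description of Statistical Methods) applies a two-sided 0.05 criterion to all analyses. It has no separate rule for interim data.

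No section says which endpoint the interims examine, whether they compare the two groups, who receives the results, or what decision could follow. Section 11 describes a Steering Committee and an Event-adjudication Committee and gives neither an interim-review role.

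On timing, section 7.1 says "Consecutive patients will be enrolled over one year of time at the participating Centers", and section 4.4.3 says "The enrolment period is 12 months after authorization of respective Ethics Committee". Section 4.5.4 says "A follow-up contact visit is planned at 30 days" after surgery, with a window of 7 days either side. The primary endpoint, as defined in section 6.1, is antiplatelet discontinuation judged at the time of surgery.

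**The concern.** Taken together, sections 7.1 and 7.2 allow the same comparison to be tested three times (at 800, at 1,500 and at the end), each time at the full 0.05. Repeated testing of accumulating data raises the chance of at least one false-positive result above the 5% used in the sample size statement.

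The second look also invites the question of what it is for. It comes when 123 of 1,623 patients remain, so it analyses nearly the final data set shortly before enrolment would reach its target. If it is a formal test, it uses error for very little new information. If it is not, the plan should say so.

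At stake is how a nominal p just under 0.05 can be read, at an interim or at the end, and whether near-final comparative results are produced without a reason.

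**Working it through.** **Inputs.** Target 1,623, looks at 800 and 1,500, 5% significance and one year of enrolment (section 7.1); two-sided 0.05 for all analyses (section 7.2); 30-day contact (section 4.5.4). The target itself cannot be reproduced, because no event rates or effect size are given. It is used here only as the denominator.

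**1. Position of the looks.**
- 800/1,623 = 0.493
- 1,500/1,623 = 0.924, leaving 1,623 − 1,500 = 123 patients (7.6%)

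**2. Time left after the 1,500th patient.** The documents do not state an accrual pattern, so this is an assumption with a range. Let cumulative accrual be proportional to t^k over 365.25 days. The time left is then [1 − (1,500/1,623)^(1/k)] × 365.25 days.
- k = 1 (uniform): 27.7 days, 4.0 weeks
- k = 1.5 (ramp-up): 18.7 days, 2.7 weeks
- k = 2 (stronger ramp-up): 14.1 days, 2.0 weeks
- k = 0.75 (fast start): 36.4 days, 5.2 weeks

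**3. Maturity of 30-day data.** Under uniform accrual the rate is 1,623/365.25 = 4.44 patients per day. At the trigger, about 30 × 4.44 = 133 of the first 1,500 would not yet have reached 30 days, even if every operation took place on the day of enrolment. Their data would mature at about the time the 1,623rd patient is enrolled, or later.

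**4. Type I error.** Assume that information is proportional to enrolment and that each look is a two-sided test at 0.05 (critical value 1.96). The test statistics are then jointly normal under the null, with correlation √(n_i/n_j) for n_i < n_j:
- 800 and 1,500: √(800/1,500) = 0.73
- 800 and final: √(800/1,623) = 0.70
- 1,500 and final: √(1,500/1,623) = 0.96

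Overall error is 1 minus the probability that every statistic lies within ±1.96:

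| Looks tested at 0.05 | Numerical integration | Simulation (3 million runs) |
|---|---|---|
| Final only | 5.0% | – |
| 800 and final | 8.3% | 8.3% |
| 1,500 and final | 6.3% | 6.3% |
| 800, 1,500 and final | 9.3% | 9.3% |

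The 800 look adds 8.3 − 5.0 = 3.3 points. The 1,500 look then adds about 0.9 more (9.27 − 8.34).

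**5. Boundaries that hold 5% with both looks kept.**
- Haybittle-Peto, absolute z above 3.29 at each interim: final nominal p about 0.0498.
- O'Brien-Fleming-type spending: nominal p of about 0.0052, 0.039 and 0.036 at the three analyses.

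**The case against.** A reader might infer that the 1,500 look cannot change the study and does nothing but add type I error. The documents do not support that.

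- **Endpoint.** The primary endpoint is fixed around surgery and does not wait for the 30-day contact; the maturity argument in step 3 applies to the secondary ischemic and bleeding endpoints. Some delay may still apply to the primary endpoint: patients are screened at preoperative evaluation (section 4.5.2), so some may not have had surgery at the trigger, and thrombotic risk is assigned only at data analysis (section 4.5.3).
- **Timing.** Four weeks rests on uniform accrual, a single 12-month calendar and closure at 1,623. Section 4.4.3 counts from each respective ethics authorization, so centres may start at different times, and 1,623 is a requirement, not a stated cap. If staggered starts stretched accrual to 18 months (an assumption), the gap would be 27.7 × 1.5, or about 41.5 days.
- **Purpose.** The absence of a stated purpose does not show that none is possible. A late look could check the matched count, or the count within one year of stenting, and inform whether to extend enrolment. The plan contains no such rule, however, and an extension made after seeing comparative results would itself need one.
- **Error.** Type I error rises only if the interims test between groups without adjustment. Section 7.2 implies this by its scope, but section 7.1 does not say what the interims test. The looks are assigned to an independent statistician, and nothing says that results are released.
- **Information.** Section 7.2 excludes some patients and applies propensity matching, so 1,500 enrolled need not be 92% of the analysable information.

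These points limit the conclusion to a conditional one. They do not supply the missing boundary or the missing purpose.

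**Conclusion.** The concern holds in conditional form. The plan schedules two interim analyses, applies an unadjusted 0.05 to all analyses, and defines no boundary. If each look tests the group comparison, and information tracks enrolment, overall type I error is about 9.3% against the stated 5%.

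Most of the excess comes from the 800 look (3.3 points); the 1,500 look adds about 0.9. It would therefore be wrong to conclude that removing the late look cures the problem.

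The lateness of the 1,500 look is a separate, smaller weakness. At 92% of the target, two to five weeks from the 1,623rd patient across the accrual shapes tried over 12 months, and with a statistic correlated 0.96 with the final one, it has little realistic scope to alter the study. This is clearest for the 30-day endpoints and weaker for the primary endpoint. The point is minor in severity and cheap to correct.

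**What to change.** In section 7.1, do one of two things for every interim retained:

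1. State that it is descriptive (for example enrolment, data completeness, matched counts) and makes no between-group test; or
2. Name the endpoint, the recipient of the results and the possible decision, and apply a boundary that keeps the total at 5%. Haybittle-Peto with absolute z above 3.29 at the interims and a final p of about 0.0498 would do this. Boundaries should be based on the analysable number if that departs from enrolment.

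Amend the general 0.05 statement in section 7.2 to refer to this rule.

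Drop the 1,500 look unless a purpose is written down for it, such as checking the matched count or the count within one year of stenting.

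The cost is a few sentences. The downside is a slightly stricter final threshold (negligible with Haybittle-Peto; about 0.036 with O'Brien-Fleming-type spending over both looks), or the loss of one late look, which also saves an analysis.
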